## Protocol Synopsis

Title	Cortical stimulation to treat mood and behavioral symptoms in Parkinson's disease patients
Study Phase	Phase I
Device(s)	
Device Information: Devices to be used in this study are grouped below according to FDA approval. All are Medtronic Devices.
 
Investigational
 
 
• Activa PC+S implantable pulse generator, Model 37604
 
• Sensing Programmer Model 8181 for Activa PC+S
 
• Sensing Programmer Software Model 8180 for Activa PC+S
 
• Lead extension Model 37087
 
• Nexus-D2/3 System
 
• Nexus-D2/3 Application Programming Interface (API)
 
• Nexus-E firmware and Activator
 
• Intercept Patient Programmer, model 37441
 
• Summit RC+S implantable pulse generator (IPG), Model B35300R
 
• Research Lab Programmer (RLP), Model 4NR010
 
• Clinician Telemetry Module (CTM), Model 4NR011
 
• Research Software Development Kit (RDK), Model 4NR013
 
• Patient Therapy Manager(PTM), Model 4NR009
 
• Recharge Therapy Manager (RTM), Model 97755
 
 
Approved for other indications
 
 
• Medtronic Resume II paddle electrode model 3587A
 
 
Approved for the intended indication
 
 
• N'Vision Clinical Programmer Model 8840
 
• Clinician Programmer Software Model 8870
 
• Patient Programmer Model 37642
 
• Lead Model 3389 or 3387
 
• External Neurostimulator 37022
 
• Lead extension model 37086
 
• Activa SC 37603 single channel pulse generator
 

Indication	Adults with Parkinson's disease (PD) who experience inadequate relief of motor symptoms in the setting of optimal medical therapy by a movement disorders neurologist, who have been offered implantation of a deep brain stimulator system and who also suffer from one or more of the following non-motor symptoms: depression, anxiety and impulsivity.

Sponsor Contact	
[name]., MD          Professor of Neurological Surgery          University of California, San Francisco          [name]          [name]          [contact]          [contact]          [contact]

Medical Safety Monitor	
The medical safety monitor (MSM) consists of a neurologist, [name] (at the University of Florida, Gainesville), outside of our home institution, who has no direct involvement in this study but who has expertise in implantable devices. Treatment related adverse events assessed as definitely, probably, or possibly related to study procedures and either serious or unexpected, noted by any study personnel will be reported within 10 working days of their knowledge of the event to the MSM. The MSM will then advise the PI on potential changes in procedures to improve safety, or, in the event of multiple serious adverse events, may invoke stopping rules.

Treatment	
Stimulation of the basal ganglia for treatment of the motor symptoms of Parkinson's disease patients, and stimulation of the prefrontal cortex for treatment of mood and behavioral symptoms.

Study Site	
University of California, San Francisco          [name]          [name]

Study Design	
This is a single-center study of the neurophysiology of non-motor symptoms such as anxiety, depression, and impulsivity that are comorbid in Parkinson's Disease.
 
The aims are to:
 
 
1) Determine the neural correlates of non-motor symptoms in PD patients.
 
2) Determine how open-loop cortical stimulation can reduce these symptoms and normalize the abnormal brain signals.
 
3) Develop closed-loop DBS paradigms by integrating the biomarkers of non-motor symptoms identified in the early phase of this project.
 
4) Teach patients how to voluntarily modulate cortical signals related to non-motor symptoms.
 
 
In addition to their standard therapeutic DBS electrode(s) used to treat their motor symptoms, patients enrolled in this study will have a flexible 4-contact electrode (Medtronic 3587A Resume II paddle lead) placed over the prefrontal cortex. This cortical electrode will be advanced through the same burr hole used for the DBS lead implants and placed on the surface of the brain in the subdural space. The cortical electrode, as well as the standard therapeutic DBS electrode implanted on that side, will be attached to a Medtronic Activa PC+S pulse

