## **9.0 Statistical Methods and Data Analysis**

LFP data will be analyzed using wide power-spectral analysis as well as analysis of specific frequency domains (i.e. in the delta, theta, alpha, beta, gamma bands). We will also examine region-specific coherence and cross-frequency coupling in addition to coherence between cortical and subcortical brain areas. Using a repeated measures ANOVA statistical analysis, summary statistics for power in relevant frequency bands, power changes, and magnitude of coupling and coherence will be compared at different time points, different DBS conditions (on and off), different medication states (on and off), in a repeated measures (within subjects) design. The small number of subjects is mitigated by the ability to study varying mood states longitudinally within each subject. We will assess the correlation between the severity of non-motor symptoms and brain physiology measures. Additionally, bootstrapping statistical applications (i.e. a Monte Carlo algorithm) and general linear mixed models can be utilized to investigate potential statistical effects, given the small sample size).

Since this is a pilot study of chronic cortical recording, the sample size is likely to be too small to provide definitive answers to all research questions. Based on this exploratory analysis, it is anticipated that the next phase of the study will focus on a subset of the research aims, with 10 subjects per group.

Sample size calculation: This is a pilot study of a novel chronic brain recording technique. The goals are to assess technique feasibility, to collect pilot data that will be used to frame more detailed hypothesis about DBS mechanisms, and (in the add-on study using Nexus-D and E) to explore potential strategies for therapeutic use of the Activa PC+S and Summit RC+S neural interface. Thus, there is no formal sample size calculation.

*Criteria for study success that would justify a larger subsequent trial:* This study will be considered to justify a larger subsequent trial if we can demonstrate:

- 1) Chronic LFP recording from the cortex, of adequate quality to assess signatures of non-motor symptoms
- 2) No permanent serious adverse events occur
- 3) Therapeutic benefit in non-motor symptoms produced by cortical stimulation (open loop or closed loop) or neurofeedback training.

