#### Data and safety monitoring plan

Treatment-emergent adverse events that are assessed by the principal investigator as possibly, probably, or definitely related to surgical implantation or chronic cortical recording AND are unexpected or meet seriousness criteria (death, immediately life threatening, hospitalization >24 hours, persistent or significant disability, or significant intervention required to prevent one of the previously-stated outcomes) will be reported to the IRB, device manufacturer and the FDA via the MedWatch online voluntary reporting form within 10 working days of the study team's knowledge of the event.

All such events will also be reported to the medical safety monitor (MSM), which consists of a neurologist, [name] (University of Florida, Gainesville), outside of our home institution, who has no direct involvement in this study but who has expertise in implantable devices. Treatment-related adverse events assessed as definitely, probably, or possibly related to study procedures and either serious or unexpected, noted by any study personnel will be reported within 10 working days of their knowledge of the event to the MSM. The MSM will then advise the PI on potential changes in procedures to improve safety, or, in the event of multiple serious adverse events, may invoke stopping rules.

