## Institutional Review Board

This protocol and relevant supporting data are to be submitted to the appropriate IRB for review and approval before the study can be initiated. Amendments to the protocol will also be submitted to the IRB prior to implementation of the change. The PI is responsible for informing the IRB of the progress of the study and for obtaining annual IRB renewal. The IRB must be informed at the time of completion of the study and should be provided with a summary of the results of the study by the PI. The PI must notify the IRB in writing of any SAE or any unexpected AE according to ICH guidelines.

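### Serious or unexpected events judged unrelated have no planned route to the medical safety monitor, although the IRB is to be told of them

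*Combined protocol and SAP*

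**What the plan says.** Four statements govern where adverse events go.

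- **Synopsis, Medical Safety Monitor.** Within 10 working days the monitor receives "Treatment related adverse events assessed as definitely, probably, or possibly related to study procedures and either serious or unexpected". The assessor is not named.
- **Data and safety monitoring plan, first paragraph.** The IRB, device manufacturer and FDA receive, within 10 working days, events "assessed by the principal investigator as possibly, probably, or definitely related to surgical implantation or chronic cortical recording" that are also unexpected or serious.
- **Data and safety monitoring plan, second paragraph.** This opens by forwarding that same set to the monitor ("All such events will also be reported to the medical safety monitor (MSM"). It then repeats the synopsis rule: "Treatment-related adverse events assessed as definitely, probably, or possibly related to study procedures and either serious or unexpected, noted by any study personnel". The monitor advises the principal investigator and, "in the event of multiple serious adverse events, may invoke stopping rules".
- **Section 10.0, Institutional Review Board.** "The PI must notify the IRB in writing of any SAE or any unexpected AE according to ICH guidelines". The monitor is not mentioned and no deadline is given.

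The synopsis also lists regular follow-up by the study psychiatrist and suicidality rating at outpatient visits. Neither is given a route to the monitor.

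**The concern.** An outside monitor is most useful where the study team's causal judgement is least certain. Here that is the psychiatric event. Section 4.0 requires a mood, anxiety or impulsivity problem at entry. The Introduction says that depression and anxiety arise from the disease itself and that impulsive behaviour often follows dopaminergic treatment. It also reports that prefrontal stimulation altered mood in patients who were anxious or depressed. A psychiatric event thus has a ready explanation outside the study and a plausible cause within it.

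If the study team settles on the first explanation and rules out even a possible study role, the plan does not ask the monitor for a second opinion. A psychiatric admission longer than 24 hours would meet the plan's definition of serious and still not be sent. At stake is whether the person who may invoke stopping sees the complete series of serious events or only the part already attributed to the study.

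**Working it through.** The plan gives no event rate, numeric stopping threshold or power calculation to reproduce. The check is a comparison of the reporting rules, followed by an illustration on assumed inputs.

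**1. The rules as sets.** Let S = serious, U = unexpected, R = at least possibly related to study procedures, and R′ = judged by the principal investigator at least possibly related to implantation or cortical recording.

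| Recipient | Source | Events sent |
|---|---|---|
| Monitor | Synopsis; monitoring plan, second paragraph | R and (S or U) |
| Monitor | Monitoring plan, forwarding sentence | R′ and (S or U) |
| IRB, manufacturer, FDA | Monitoring plan, first paragraph | R′ and (S or U) |
| IRB | Section 10.0 | S or U |

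**2. What the monitor does not get.** Implantation and recording are study procedures, so R′ lies within R and the forwarding sentence adds nothing. Subtracting the monitor's set from the section 10.0 set leaves (S or U) and not R. These events go to the IRB and have no written route to the monitor.

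**3. Wording inside the monitoring plan.** R′ does not name stimulation. Read literally, an event thought possibly due to stimulation alone falls outside the first paragraph. It reaches the monitor only through the broader wording of the second, provided stimulation counts as a study procedure.

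**4. What goes to the IRB.** The monitoring plan sends the IRB related events only; section 10.0 sends it all serious and all unexpected events. The first could be a timed subset of the second, but the protocol does not say so.

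**5. Can the attribution be checked within the trial?** There is no parallel control group. Table 2 has within-patient sessions of brief cortical stimulation (under 2 hours) off, on, then off at visits 7-10. Section 6.0 offers an optional blinded active-versus-sham test, 1 hour a day for 14 days. Neither can settle the cause of a rare serious event during 5 years of follow-up.

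**6. Size.** Suppose, as assumptions only, that each of the 10 patients has risk p of a serious psychiatric event, a share r of such events is judged at least possibly related, patients and judgements are independent, and two affected patients count as multiple. The chance that the monitor is sent events from at least two patients is

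1 − (1 − pr)^10 − 10·pr·(1 − pr)^9.

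For p = 0.20 and r = 0.5, pr = 0.10, giving 1 − 0.349 − 0.387 = 0.264.

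| p | r = 1 | r = 0.75 | r = 0.5 | r = 0.25 | r = 0 |
|---|---|---|---|---|---|
| 0.10 | 0.264 | 0.170 | 0.086 | 0.025 | 0 |
| 0.20 | 0.624 | 0.456 | 0.264 | 0.086 | 0 |
| 0.30 | 0.851 | 0.695 | 0.456 | 0.170 | 0 |

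The r = 1 column is also the result when no event is filtered out. The loss runs from none to total depending on r, on which the documents are silent. With one assessor making most judgements, independence is doubtful too.

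**The case against.** The case for leaving the rule alone has substance. A possible relation is enough, and any study personnel may note the event, so only events judged not even possibly related fall outside. Nothing bars the principal investigator from telling the monitor more. The IRB is told of every serious event under section 10.0, and a psychiatrist follows each patient. Appendices C (Case Report Form) and D (Risk Assessment) have no content in the text reviewed, so a further reporting route there cannot be excluded. All of this stands and narrows the gap. It does not close it: a notice to the IRB puts nothing in front of the monitor, and what remains outside is the group for which a second causal opinion would be new information.

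Three stronger readings are tempting, and the documents do not support them.

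- **That such events can never reach the monitor or count toward stopping.** The stopping clause refers to multiple serious events without a relatedness limit, so an unrelated event the monitor learned of could count. The synopsis names no assessor. The principal investigator is named only in the sentence on IRB, manufacturer and FDA reports, so that role as gatekeeper for every monitor report is an inference.
- **That the monitor is the only independent oversight.** The IRB, FDA and manufacturer also receive reports, and the IRB grants annual renewal.
- **That the stopping trigger conflicts with the second success criterion**, "No permanent serious adverse events occur". That criterion helps decide, at the end, whether a larger trial is justified; the trigger concerns stopping during the study. They need not match. Non-permanent serious events also count toward the trigger, and the monitor is already to advise after reported events.

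**Conclusion.** The concern holds in a limited form. By the plan's own wording, a serious or unexpected event judged not even possibly related has no planned route to the medical safety monitor, although section 10.0 requires the IRB to be told of it. This is a stated rule, repeated in two places, and not merely missing detail. It matters here because the entry symptoms offer a ready alternative cause for psychiatric events and the design gives little means of testing that attribution.

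The direction needs no numerical assumption. The size cannot be derived from the documents, and the table above shows only how far it depends on the unknown share judged related. Separately, the relatedness wording within the monitoring plan and the two statements of IRB reporting scope do not agree as written.

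**What to change.** 1. In the synopsis and in the data and safety monitoring plan, send the monitor every serious and every unexpected adverse event regardless of attribution, together with the investigator's attribution.
2. Have the monitor record an independent attribution for each event.
3. Reconcile the relatedness wording in the monitoring plan, so that its first and second paragraphs refer to the same exposures and it is clear whether stimulation is covered.
4. Reconcile the IRB reporting scope between the monitoring plan and section 10.0, stating whether the former is a timed subset of the latter.

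No stopping threshold is proposed; that is for the sponsor and the monitor. The cost is one amended reporting sentence in two places, two clarifications, and a few more reports to a monitor already in post, for 10 patients whose serious and unexpected events must already be reported to the IRB.

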Objectives	
In ten patients undergoing DBS implantation for PD, we will implant a subdural cortical electrode in addition to the DBS electrode, and connect these to a novel implantable pulse generator that can store / stream field potential data (Medtronic Activa PC+S, Medtronic Summit RC+S). At multiple time points post-implantation up to 5 years, in our clinic or patients' homes, cortical and subcortical signals will be recorded. Data will be collected while patients are resting or engaged in emotion/cognition tasks and while cortical stimulation on and off. In addition to brain signals recordings, symptoms will be assessed using validated questionnaires and tasks to allow identification of neurophysiological correlates of non-motor symptoms. These signals will be used to determine the optimal stimulation parameters to disrupt symptom-related neural activity, and to implement feedback-controlled cortical stimulation
 
Hypotheses:
 
 
1) Characteristics of the prefrontal ECoG potentials (spectral power in specific bands, interaction between different frequency bands and/or between brain regions) correlate with severity of non-motor symptoms
 

	
2) For patients who have non-motor fluctuations in mood, anxiety, or impulsivity in response to dopaminergic medication, characteristics of the prefrontal ECoG potentials will vary in relation to medication state.
 
3) Cortical stimulation can reduce the severity of non-motor symptoms
 
4) Patients can learn how to voluntarily modulate cortical signals related to non-motor symptoms

Patient Population	Study subjects will be adults with Parkinson's disease (PD) deemed appropriate candidates for the treatment of motor symptoms using deep brain stimulation. Study subjects will also have one or more of the following non-motor symptoms: depression, anxiety, or impulsive behavior.
Sample Size	10 subjects
Efficacy Assessments	Non-motor symptoms will be assessed by validated questionnaires: BDI= Beck Depression Inventory, BAI= Beck Anxiety Inventory, HADS= Hospital Anxiety and Depression Scale, QUIP= Questionnaire for Impulsive-Compulsive Disorders in Parkinson's Disease, YBOCS= Yale-Brown Obsessive Compulsive Scale. Since these scales assess symptoms over the previous few weeks period, visual analogue scales (VAS) will be used to assess the non-motor symptoms at the time of the recordings. In addition, objective measure such as blood pressure, electrodermal activity, electromyography and/or task performance such as reaction time and error rate might also be used to assess non-motor symptoms.
Safety Assessments	
1) Physical examination at all study visits
 
2) Baseline evaluation and regular clinical follow up with the study psychiatrist
 
3) Check of pulse generator stimulation parameters, impedance measurements, and battery voltage at all study visits
 
4) Surgical or nonsurgical adverse events as recorded on case report forms
 
5) Assessment of suicidality using the Columbia Suicide Severity Rating Scale, at protocol-defined outpatient visits
 
6) In visits where the Nexus D and/or E system will be used for closed loop stimulation, all possible stimulation settings are preselected by clinicians to avoid the possibility of producing major stimulation-induced adverse effects
 
7) When closed loop stimulation is used out of the clinic, patients can exit closed loop mode at any time, using a hand-held controller, and return to their normal clinical settings

## 1.0 Introduction

Parkinson's disease (PD) is a common neurological disorder characterized by a constellation of motor and non-motor features, including cognitive and psychiatric symptoms.

Motor symptoms in PD have been well studied and several treatment options exist for their amelioration. One common treatment is deep brain stimulation (DBS), in which electrical stimulation is delivered through electrodes implanted in deep structures of the brain in order to modulate neural circuits. The two most important limitations of DBS currently used to treat PD are: 1) It does not treat non-motor features of the disease, and 2) contemporary DBS devices deliver "open loop" stimulation that is continuously on, and is unresponsive to fluctuations in brain physiology. 'On demand' or "closed loop" therapy is likely to overcome the limitations of the current 'open-loop' paradigm, reducing the side effects of stimulation and duration of programming sessions that are based on trial and error (1, 2). Both of these limitations are addressed in this protocol.

Depression and anxiety are among the most prominent non-motor symptoms in PD and greatly affect patients' and caregivers' quality of life. They occur organically as part of the fundamental circuit disruption of PD and often predate motor impairment (3, 4). In addition, impulsive behaviors frequently follow the addition of dopaminergic therapy (5). Increasingly recognized in PD is the development of impulse control disorders (ICD) such as gambling, hypersexuality, or punding. A subset of PD patients also suffers from a form of addiction, dopamine dysregulation syndrome (DDS), in which patients compulsively self-medicate with excessive doses of dopaminergic medication (6, 7). In total, these neuropsychiatric symptoms affect 35% of PD patients. In contrast to the motor symptoms, the pathophysiology of non-motor symptoms in PD is largely unknown. None of the currently available therapies for the motor signs of PD (i.e. dopaminergic medication, DBS) alleviate these symptoms. It is therefore crucial to investigate the pathophysiology underlying these symptoms in order to develop a comprehensive treatment for these patients. **We thus aim to identify neurophysiological signatures of non-motor symptoms in PD, and then incorporate these biomarkers in closed-loop stimulation paradigms and neurofeedback training to treat these symptoms.**

In PD, the progressive degeneration of dopaminergic neurons in the substantia nigra pars compacta leads to a depletion of dopamine, the principal neurotransmitter of both the nigrostriatal and the mesolimbic systems. The latter is associated with cognitive control, as well as emotional and motivational processes. A key structure in this limbic circuit is the prefrontal cortex (PFC). The PFC is involved in decision making, regulation of the emotional state in normal individuals, and in evaluating and comparing the expected rewards or punishments of an action (8-10). These mechanisms are essential for adaptive learning and their failure can lead to the inappropriate behavioral selection that can give rise to the mood and impulse control disorders often observed in PD (11, 12).

We will evaluate limbic circuits through chronic recording from the prefrontal cortex using a subdural strip lead, and manipulate this network using open and closed-loop cortical stimulation. Our extensive experience with intraoperative cortical recordings and acute brain stimulation supports the importance of PFC in these non-motor symptoms. We have also shown that acute intraoperative delivery of stimulation pulses in the PFC can induce a positive affect in PD (unpublished data). More importantly we showed that

this stimulation modulates mood in patients who were anxious or depressed at the time of stimulation, but did not induce changes in patients without these symptoms. Based on the literature and our results, PFC is a promising candidate for the development of a closed-loop stimulation paradigm to treat psychiatric symptoms.

This new study will utilize several investigational devices, as well as devices approved for other indications. We will use the investigational Medtronic Activa PC+S or Medtronic Summit RC+S implanted device, sensing programmer and associated software (13). The Activa PC+S is based on the FDA-approved Activa PC neurostimulator, but consists of additional sensing, stimulation and detection features (14). We will also use Medtronic's Nexus technology to develop closed-loop stimulation algorithms. Nexus D2/D3 systems are investigational devices providing a bidirectional, noninvasive interface between the Activa PC+S implanted device and an external computer. They mediate data streaming in real-time from the Activa PC+S to an external computer that extracts metrics that may be relevant to non-motor and behavioral symptoms (such as spectral power, coherence between brain regions or cross frequency interactions, such as phase-amplitude coupling (PAC)) and automatically adjusts the stimulation settings in the PC+S device, based on these metrics. Nexus E system allows for uploading fully closed-loop stimulation paradigms onto PC+S, without data streaming. The stimulation settings adjustments will always remain within allowable settings pre-programmed by a clinician using standard procedures (i.e. using the Medtronic 8840 programmer). Using Nexus-D2/3 and E, patients will also be trained to voluntarily modulate their abnormal signal in a way that minimizes their symptoms. The Summit RC+S is the second-generation bi-directional (sense and stimulate) interface which has a rechargeable battery, and an improved signal to noise ratio allowing detection of high frequency brain signals. It also has greater flexibility in the implementation of adaptive algorithms. All investigational devices contain the required statement: "CAUTION-Investigational Device. Limited by Federal Law to Investigational Use" and contain adequate information for the proposed investigational study, in accordance with § 812.5(a).

